a way to further protect the participant and also give them an opportunity to take part in the study if their physician deems it appropriate and safe. At the initial screening, any participant with a primary care physician and/or psychiatrist external to VA will be asked to sign a release of information allowing us to contact a primary care physician or other treating physician (including psychiatrist when applicable) regarding participation in the study. In the screening session, if a participant indicates a medical problem that is a contraindication to NRT or bupropion, as determined by the study physician, we will contact the physician(s) identified in the signed releases of information. Physician(s) external to VA will be contacted by fax using an approved cover sheet and an IRB approved physician letter. If the physician identified in the release of information is a physician located on site at the Durham VA Medical Center, we will contact the physician via email (as is consistent with existing privacy policies at the medical center). Physicians will be asked to email or fax back their approval of participation to a fax machine located in [name] research laboratory. Only members of the research staff listed on the staff listing for this protocol have access to this fax machine. If the request is not returned within two weeks, the study physician will determine eligibility.

Any participant who will not be stable on their medications for the study period, has a history of myocardial infarction in the past 6 months, has a contraindication to NRT and is unable to get medical clearance from their primary care provider will be excluded. If potential participants use any other forms of nicotine such as cigars, pipes, or chewing tobacco, they will be excluded from participation. For safety and informed consent reasons, fluent conversational English will be required of all participants. Adolescent smoking is a phenomenon worth investigating but given both ethical and feasibility issues, we will not include children or adolescents under age 18 in this study.

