## Summary of Inclusion Exclusion Criteria

To be enrolled in this study, participants must have the following characteristics:

- Veteran
- Be current cigarette smokers of at least ten cigarettes a day.
- Meet criteria for current PTSD.
- Speak and write fluent conversational English.
- Be between 18 and 75 years of age.
- Be willing to attempt smoking cessation.

Potential participants will be excluded from participating in this study for the following reasons:

- Screened participants will not be stable on their medications for the study period
- Screened participants who have a history of myocardial infarction in the past 6 months
- Screened participants who have a contraindication to NRT and are unable to get medical clearance from their primary care provider will be excluded.

- Screened participants who use any other forms of tobacco such as cigars, pipes, or chewing tobacco and are unwilling to stop using.
- Pregnancy
- Inability to complete study measures and tasks independently
- Dementia or other brain disorder, schizophrenia, current manic syndrome, or substance abuse/dependence in the preceding 3 months.
- Currently receiving trauma-focused psychotherapy.
- Currently enrolled in another smoking cessation trial.
- Currently living in court-ordered residential substance abuse treatment.

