## Screening Session

Potential participants will complete a phone screen to determine whether they might be eligible for the study. Remaining potential participants will be scheduled for a full screening session, lasting approximately 5 hours total (30 minutes consent; 4.5 hours study procedures). For the screening session, participants will meet a member of the research team at the Nicotine Research Laboratory at the Durham VA. The study will be explained in detail, and the participants will provide informed consent.

As indicated in the informed consent form and HIPAA authorization, the following information will be collected: Name; address; phone number; age; birth date; social security number; dates of study visits; dates of traumatic events; current health and mental health conditions; alcohol/drug abuse current status and history; medical history information; current medications; smoking status; number of cigarettes smoked per day; pregnancy; traumatic event; veteran status; lab results (saliva analysis, urine drug screen, pregnancy screen); questionnaires; structured clinical interviews; descriptions of traumatic life events; medical chart review, and traumatic data collected at each session during study participation.

Urine samples will be collected for drug screen urinalysis and will be disposed after we obtain the urinalysis chemistry report. Urine drug screens will be used to corroborate self-report of substance use; the presence of substance use disorders is determined by clinical interview (see below). The participant will then provide a breath sample in order to assess CO level and a saliva sample for assessing salivary cotinine, a metabolite of nicotine. Study staff will measure the participant's height and weight in order to

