As part of the screening session, participants will be asked to fill out several questionnaires: PTSD symptom severity will be measured by the PTSD Checklist (PCL) (Weathers, Litz, et al., 2013), depressive symptoms will be measured by the Beck Depression Inventory (BDI-II) (Beck, Steer, & Brown, 1996), and perceived Self-Efficacy will be assessed with the Relapse Situation Efficacy Questionnaire (RSEQ) (Gwaltney, et al., 2001), and affective states will be assessed by the Positive and Negative Affect Schedule (PANAS) (Watson, Clark, & Tellegen, 1988). Information about minority, racial and marital status, medications, medical history, years of education and age will be collected. Participants' socioeconomic status will be measured using the Objective Socioeconomic Status measure (OSS; Adler, Epel, et al, 2000). General life satisfaction will be measured with the Quality of Life Inventory (Frisch et al., 1992). Information about nicotine dependence using the Fagerström Test of Nicotine Dependence (FTND) (Heatherton, Kozlowski, Frecker, & Fagerström, 1991), a stages of change measure (Prochaska and Diclemente, 1983), a question regarding motivation to quit smoking, and the Minnesota Nicotine Withdrawal Scale (MNWS) (Patten & Martin, 1996). General desire to smoke will be measured using the 32-item Questionnaire on Smoking Urges (QSU) (Tiffany & Drobes, 1991). Subjects will report about general smoking exposure history using the Smoking Exposure Questionnaire, and will report regarding electronic cigarette use on an internally designed measure. Participants will complete the Connor-Davidson Resilience Scale (CD-RISC). The CD-RISC is comprised of 25 5-point Likert-type items designed to measure an individual's range of abilities to manage different types of stress (Connor and Davidson 2003). In order to evaluate sleep quality and sleep problems, we will ask participants to complete the Pittsburgh Sleep Quality Index with

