### Assessments After Screening

Prior to each session, participants will complete questionnaires to assess psychiatric symptoms and smoking variables. These include the PTSD checklist (PCL), questions about smoking behavior in the past week, and the Beck Depression Inventory (BDI-II). In the final two sessions, participants will also complete the ASI, QOLI, TRGI, PSQI-A, CAPS, treatment satisfaction, Cook Medley Hostility Scale, e-cigarette use measure, and a question about current non-study psychotherapy. In session 8, participants will complete measures of treatment credibility and expectancy using the Reaction to Treatment Questionnaire (Borkovec & Nau, 1972). At the beginning and end of treatment, therapists will rate their level of allegiance to the therapy they are using with a single question asking "Which treatment do you think leads to better outcomes?" In the final treatment session, participants will also complete measures of SmokeFreeVet usability, and the nicotine dependence stages of change measure. In session 14 (after the final treatment session), participants will be interviewed with the CAPS.

Abstinence and relapse will be monitored by ED entries and at visits 7-14. Participants will provide breath samples for carbon monoxide (CO) analysis at every laboratory visit following their quit date. The first verification of smoking abstinence will occur on the morning following their quit date. Smoking abstinence will be obtained by self-report and verified by comparing CO levels to the level obtained at the baseline visit. The chart below lists the sliding scale of CO values that will be considered validating. At the six month follow-up visit, salivary cotinine will also be used to confirm self-reported

smoking abstinence. The formula in Table 1 below uses the participant's CO reading at the screening visit to determine the threshold that will be considered as confirming smoking abstinence after the quit date for each participant.

Table 1. Carbon Monoxide Thresholds for Validating Smoking Abstinence			
CO SCREENING	AM CO LIMIT		
		AM CO Limit after Overnight	
14-15	15	Abstinence	
16-18	16	AM CO Limit Formula: [14 + (.25 *	
19-21	17	(1.33 * (SCREENCO -14)))]	
22-24	18		
25-27	19		
28-30	20		
31-33	21		
34-36	22		
37-39	23		
40-42	24		
43-45	25		
46-48	26		
49-51	27		
52-54	28		
55-57	29		
58-60	30		
61-63	31		
64-66	32		
67	33		

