After saliva samples are returned to the research laboratory, they will be sent for analysis to the University of California at San Francisco Pharmacology Laboratory for analysis. Should this laboratory discontinue salivary assay analysis, or should the PI determine use of another lab is warranted for this purpose, another lab will be identified to provide this service and this new lab will be reported to the IRB. Coded samples will be sent by trained study team members in accordance with the standards of practice outlined in Research Transporting and Shipping Biological Specimens, SRS SOP 202. Saliva samples will be analyzed for the presence of cotinine using a standard cut point off 10 ng/ml to determine abstinence. A blind sample of 5% will be run again to assure test accuracy of saliva samples. Secondary smoking outcomes will include 7-and 30-day point prevalence abstinence at each assessment, where abstinence is defined as no tobacco use in the prior 7 or 30 days respectively (McFall et al., 2010)

Any participant who is unable to remain abstinent from smoking after their quit date will be encouraged to make additional quit attempts. Participants will be allowed to make as many quit attempts as necessary during their study enrollment until they are successful or until they have completed their study enrollment. There will be no additional sessions provided for those participants who do not remain abstinent.

Consistent with guidelines for Integrated Care for Smoking Cessation, participants will continue to receive brief care for smoking cessation for as long as they remain in therapy for PTSD. In the CPT-C and smoking condition, this means that study session 8 will be the first session of smoking cessation counseling that will focus on relapse prevention and encouraging those who have relapsed to make an additional attempt to stop smoking. In sessions 8-13, participants will complete questionnaires to assess psychiatric symptoms and smoking variables and continue to receive smoking cessation follow-up counseling. In the smoking cessation condition, participants will complete the six sessions included in the Integrated Care for Smoking Cessation manual, as well as completing brief smoking counseling when completing assessments at study sessions following the quit attempt.

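### Eligibility of people who use other nicotine or tobacco is stated in two conflicting ways, e-cigarettes are left undecided, and the 6-month cotinine check has no rule for non-tobacco nicotine

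*Combined protocol and SAP*

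**What the plan says.** On eligibility, the Population section gives a flat exclusion: "If potential participants use any other forms of nicotine such as cigars, pipes, or chewing tobacco, they will be excluded from participation". The Summary of Inclusion Exclusion Criteria lists a conditional one: "Screened participants who use any other forms of tobacco such as cigars, pipes, or chewing tobacco and are unwilling to stop using". Neither section refers to the other on this point or says which prevails.

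On e-cigarettes, the Screening Session section says participants "will report regarding electronic cigarette use on an internally designed measure", and Assessments After Screening repeats the measure in the final two sessions. Neither eligibility rule mentions them.

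On verifying abstinence, Assessments After Screening provides for CO throughout: "Participants will provide breath samples for carbon monoxide (CO) analysis at every laboratory visit following their quit date". Cotinine, which the Screening Session section describes as "salivary cotinine, a metabolite of nicotine", is added late: "At the six month follow-up visit, salivary cotinine will also be used to confirm self-reported" smoking abstinence. The threshold is fixed: "Saliva samples will be analyzed for the presence of cotinine using a standard cut point off 10 ng/ml to determine abstinence". For the secondary 7- and 30-day point-prevalence outcomes, "abstinence is defined as no tobacco use in the prior 7 or 30 days respectively".

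Two further provisions bear on this. The Nicotine Replacement Therapy section allows a participant who has not stayed abstinent to restart NRT during follow-up. Under Data Analysis and Hypotheses, Hypothesis 3 places the main smoking analysis at Week 6 and makes 6-month cessation a secondary analysis.

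**The concern.** An eligibility rule has to give one answer for one person. Here screening staff can reach opposite decisions about the same veteran, depending on which section they consult. Who enrols could then vary with the reader, and the enrolled population could not be described accurately afterwards. This matters most for Hypothesis 3, which is framed against published figures for VA usual care. Randomisation does not protect a comparison with an outside source, so the make-up of the sample bears on it directly.

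The change from nicotine to tobacco opens a second gap. Someone who smokes cigarettes and also vapes can be read as excluded by the first rule and admitted by the second with no condition about stopping.

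A related question arises at six months. Cotinine shows exposure to nicotine, not to smoke. A participant who has quit tobacco but takes nicotine from a non-tobacco source may exceed 10 ng/ml and fail confirmation. The plan has no rule for that case.

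**Working it through.** The plan states no figure on this point to reproduce, so the check is a comparison of the texts.

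**Step 1: apply both rules to each kind of cigarette smoker.**

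| Candidate also uses | Population section | Summary of criteria |
|---|---|---|
| No other product | Not excluded | Not excluded |
| Cigars, pipe or chewing tobacco, unwilling to stop | Excluded | Excluded |
| Cigars, pipe or chewing tobacco, willing to stop | Excluded | Not excluded |
| E-cigarettes only | Excluded on a literal reading of nicotine | Not covered, unless e-cigarettes count as tobacco |

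The third row is a direct contradiction. The fourth is undecided: both rules give the same three tobacco examples, and neither says whether vaping counts. The neighbouring exclusions in the Summary (unstable medication, recent infarction, NRT contraindication) follow the Population text in the same order. The conflict is therefore specific to this item.

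**Step 2: follow each kind of participant to the 6-month cotinine test.**

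| State at six months | Expected cotinine | Against the no-tobacco definition |
|---|---|---|
| Quit cigarettes and stopped the other product | No contribution from that product | Classed correctly as abstinent |
| Quit cigarettes, uses cigars, pipe or chewing tobacco | Can exceed 10 ng/ml | Classed correctly as not abstinent |
| Quit all tobacco, uses e-cigarettes | Can exceed 10 ng/ml | May be classed as smoking without having smoked |
| Quit all tobacco, on restarted NRT | Can exceed 10 ng/ml | May be classed as smoking without having smoked |

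Only the last two rows are a problem, and in both the nicotine does not come from tobacco.

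**Step 3: locate the affected analysis.** Cotinine is described as a verification tool only at the 6-month visit. Earlier visits rely on self-report and CO, so the Week-6 analysis is not reached through cotinine.

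**Step 4: scale.** The share of candidates whom the two rules would classify differently is not given. For scale only, assume 5% to 20%:

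- of the 120 to be recruited: 120 × 0.05 = 6 to 120 × 0.20 = 24;
- of 50 enrolled: 50 × 0.05 = 2.5 to 50 × 0.20 = 10;
- of 70 enrolled: 70 × 0.05 = 3.5 to 70 × 0.20 = 14.

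The enrolment figures 50 and 70 both stand in the Population section. One reclassified participant moves the overall 6-month abstinence rate by 1/70 = 1.4 to 1/50 = 2.0 percentage points. If allocation is equal (an assumption), it moves one arm's rate by 1/35 = 2.9 to 1/25 = 4.0 points. How many participants would be reclassified cannot be derived from the documents.

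**The case against.** A reader might infer that admitting other-tobacco users undermines cotinine verification, and that the flat exclusion would avoid the misclassification. The documents do not support this, for three reasons.

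- The conditional rule admits only people not unwilling to stop. Those who stop carry no cotinine from that product at six months. Those who resume are using tobacco, so a positive test agrees with the point-prevalence definition. Two reservations remain: willingness at screening is not proof of stopping, and the separate reference to smoking abstinence leaves a cigarettes-only reading open. That makes an effect possible, not established.
- Eligibility is judged at screening. A participant with no other nicotine use at entry may take up e-cigarettes later, and NRT may be restarted in follow-up. Neither rule prevents either.
- The affected outcome is secondary. Hypotheses 1 and 2, on PTSD and depression, do not use cotinine.

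Eligibility is also settled before randomisation, so the conflict does not by itself favour an arm. It might further be said that recording e-cigarette use does not show that the plan expects vapers at entry, because the measure is repeated late and may be there to detect uptake during quitting. That is fair. It limits what can be inferred about intent, but leaves their eligibility undecided.

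Finally, letting a report of other nicotine use replace cotinine with CO could count a current chewing-tobacco user as abstinent. This objection stands in full, and any CO fallback has to be confined to non-tobacco nicotine.

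**Conclusion.** The contradiction holds on the face of the text and should be corrected. The two sections give opposite decisions for a user of other tobacco who is willing to stop, they differ in scope, and e-cigarette users are covered clearly by neither. This is an internal inconsistency in a rule that staff must apply, and it rests on no assumption.

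The cotinine point is separate and narrower. It concerns the 6-month secondary outcome only, and participants who have quit tobacco but use e-cigarettes or restarted NRT. The effect there is possible; nothing in the documents shows that it will occur. It also does not depend on which eligibility rule is adopted.

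The size is unknown. The 5% to 20% above is an assumption for scale, and a claim that quit rates would shift by some stated amount would go beyond the documents. The Week-6 analysis is unaffected through cotinine.

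**What to change.** 1. Reconcile the Population section and the Summary of Inclusion Exclusion Criteria into one rule with the same wording in both. State whether it covers nicotine or tobacco, and whether e-cigarette users are eligible. Which rule to adopt is for the investigators to decide.

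2. Add a short rule to the 6-month outcome definition. If a participant reports no tobacco use and the only reported nicotine source is e-cigarettes or restarted NRT, verify abstinence by self-report plus the CO reading already collected. Report the cotinine-only result for all participants as a sensitivity analysis. Keep cotinine at 10 ng/ml for everyone else, including users of other tobacco, in line with the no-tobacco definition.

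3. Confirm that the e-cigarette measure and current NRT use are recorded at the 6-month visit, since the rule depends on them.

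The cost is amendment wording and a few lines in the outcome definition, with no new laboratory test. The statistical price is that CO is a weaker check than cotinine in those few participants, and that a self-report decides who receives it. The sensitivity analysis shows how much the result depends on that choice.

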## Summary of Inclusion Exclusion Criteria

To be enrolled in this study, participants must have the following characteristics:

- Veteran
- Be current cigarette smokers of at least ten cigarettes a day.
- Meet criteria for current PTSD.
- Speak and write fluent conversational English.
- Be between 18 and 75 years of age.
- Be willing to attempt smoking cessation.

Potential participants will be excluded from participating in this study for the following reasons:

- Screened participants will not be stable on their medications for the study period
- Screened participants who have a history of myocardial infarction in the past 6 months
- Screened participants who have a contraindication to NRT and are unable to get medical clearance from their primary care provider will be excluded.

- Screened participants who use any other forms of tobacco such as cigars, pipes, or chewing tobacco and are unwilling to stop using.
- Pregnancy
- Inability to complete study measures and tasks independently
- Dementia or other brain disorder, schizophrenia, current manic syndrome, or substance abuse/dependence in the preceding 3 months.
- Currently receiving trauma-focused psychotherapy.
- Currently enrolled in another smoking cessation trial.
- Currently living in court-ordered residential substance abuse treatment.

### **Procedures**

Participants will be recruited to participate in an intervention consisting of the smoking cessation + CPT-C or smoking cessation without concurrent CPT-C. Potential participants will complete a phone screen with study personnel to rule out those who are likely ineligible. Participants will be asked to attend a total of 15 study sessions, including a screening session, counseling and/or assessment sessions (a total of 12 counseling sessions and a 1-week post-treatment follow-up in each condition), and a 6 month follow-up to verify smoking abstinence and complete assessments.

## Screening Session

Potential participants will complete a phone screen to determine whether they might be eligible for the study. Remaining potential participants will be scheduled for a full screening session, lasting approximately 5 hours total (30 minutes consent; 4.5 hours study procedures). For the screening session, participants will meet a member of the research team at the Nicotine Research Laboratory at the Durham VA. The study will be explained in detail, and the participants will provide informed consent.

As indicated in the informed consent form and HIPAA authorization, the following information will be collected: Name; address; phone number; age; birth date; social security number; dates of study visits; dates of traumatic events; current health and mental health conditions; alcohol/drug abuse current status and history; medical history information; current medications; smoking status; number of cigarettes smoked per day; pregnancy; traumatic event; veteran status; lab results (saliva analysis, urine drug screen, pregnancy screen); questionnaires; structured clinical interviews; descriptions of traumatic life events; medical chart review, and traumatic data collected at each session during study participation.

Urine samples will be collected for drug screen urinalysis and will be disposed after we obtain the urinalysis chemistry report. Urine drug screens will be used to corroborate self-report of substance use; the presence of substance use disorders is determined by clinical interview (see below). The participant will then provide a breath sample in order to assess CO level and a saliva sample for assessing salivary cotinine, a metabolite of nicotine. Study staff will measure the participant's height and weight in order to

establish a baseline to determine post-quit weight gain. Blood tests will be conducted to rule out pregnancy in pre-menopausal or peri-menopausal women. The Structured Clinical Interview for DSM-IV Diagnosis (SCID-IV) and the Clinician Administered PTSD Scale (CAPS; Weathers, Blake et al., 2013) will be administered in order to determine participant eligibility. Participants will complete the Traumatic Life Events Questionnaire (TLEQ; Kubany, Haynes et al. 2000) and the Trauma-Related Guilt Inventory (TRGI; Kubany, 1996) to provide a thorough trauma history and evaluation of its impact. If any participant indicates a possible contraindication to the use of nicotine replacement therapy, authorization to participate in the study will be obtained via medical clearance from their primary care provider. The Good Health Screening Measure and Letter to Physician for Medical Clearance are included in Appendix A: Study Measures. Participants who will be unable to complete study measures and tasks independently will also be excluded. To maximize ecological validity, participants will not be excluded if they are already receiving PTSD treatment unless it is a trauma-focused psychotherapy.

Blood samples will be collected to test for pregnancy in female participants of childbearing potential. There is minimal risk associated with venipuncture, including the possibility of infection, superficial hematoma, bleeding, clotting, and fainting. All blood samples will be analyzed at the Durham VA Medical Center and will not be transported off site.

As part of the screening session, participants will be asked to fill out several questionnaires: PTSD symptom severity will be measured by the PTSD Checklist (PCL) (Weathers, Litz, et al., 2013), depressive symptoms will be measured by the Beck Depression Inventory (BDI-II) (Beck, Steer, & Brown, 1996), and perceived Self-Efficacy will be assessed with the Relapse Situation Efficacy Questionnaire (RSEQ) (Gwaltney, et al., 2001), and affective states will be assessed by the Positive and Negative Affect Schedule (PANAS) (Watson, Clark, & Tellegen, 1988). Information about minority, racial and marital status, medications, medical history, years of education and age will be collected. Participants' socioeconomic status will be measured using the Objective Socioeconomic Status measure (OSS; Adler, Epel, et al, 2000). General life satisfaction will be measured with the Quality of Life Inventory (Frisch et al., 1992). Information about nicotine dependence using the Fagerström Test of Nicotine Dependence (FTND) (Heatherton, Kozlowski, Frecker, & Fagerström, 1991), a stages of change measure (Prochaska and Diclemente, 1983), a question regarding motivation to quit smoking, and the Minnesota Nicotine Withdrawal Scale (MNWS) (Patten & Martin, 1996). General desire to smoke will be measured using the 32-item Questionnaire on Smoking Urges (QSU) (Tiffany & Drobes, 1991). Subjects will report about general smoking exposure history using the Smoking Exposure Questionnaire, and will report regarding electronic cigarette use on an internally designed measure. Participants will complete the Connor-Davidson Resilience Scale (CD-RISC). The CD-RISC is comprised of 25 5-point Likert-type items designed to measure an individual's range of abilities to manage different types of stress (Connor and Davidson 2003). In order to evaluate sleep quality and sleep problems, we will ask participants to complete the Pittsburgh Sleep Quality Index with

PTSD Addendum (PSQI-A; Buysse, Reynolds, Monk, Berman, & Kupfer, 1989; Germain, Hall, Krakow, Shear, & Buysse, 2005). Participants will also complete the Anxiety Sensitivity Index-R (ASI-R), a 36-item 4-point Likert scale measure that assesses an individual's concerns about the emotional *and physical* consequences of experiencing anxiety symptoms. In addition, participants will complete the Cook-Medley Hostility Scale, a measure of hostile attitude, and a basic needs questionnaire designed to measure financial stability. History of head injury will be assessed with the OSU-TBI-Short Form, a short structured interview designed to detect multiple forms of traumatic brain injury (Corrigan & Bogner, 2007). Participants will be paid \$50 for screening.

With subjects' written consent, contact information containing identifying information such as name, address, phone number, and dates of research participation along with diagnostic information will be added into a "Contact Database". The purpose of this database is to re-contact potential subjects about future studies for which they may qualify. Potential participants will only be contacted about future studies under the direction of [name] and her staff. Only [name] and her research staff will have access to this database, which will be housed on the VA Network's S:\ Drive (path S:\Nicotine Research\Study Information\Study Logbooks).

Diagnostic, demographic, and questionnaire data and other information collected as part of this study will be added to a larger database entitled 'Trauma Database.' Data coding and complete confidentiality of all subject information in the "Trauma Database" will be accomplished in a three-step process. First, information from this study will be coded and will only be linked by an assigned random study number. Second, information collected from other protocols run by [name] will be coded and linked by the random study number. Lastly, the information will be merged into the larger "Trauma Database" which will be used for future research. Information collected from many study participants (500 or more) from different studies will then be examined to inform researchers about the topic they are trying to learn more about. Topics of research change over time and for that reason, the development of a combined research database is particularly useful. The purpose of combining information collected from numerous studies is to increase the power of the statistical analysis of genetic, diagnostic, questionnaire and other assessment data. Each study that deposits data into the 'Trauma Database' repository will not include any of the 18 individual identifiers under the Privacy Rule.

